Appendix C RECIST and Immune-Related Response Criteria

For this study, both RECIST v1.1 and RECIST-based irRC data will be collected but only irRC will be used to determine disease progression. Full RECIST definitions are included in the Study Reference Manual.

The irRC was originally developed using the World Health Organization (WHO) tumor response measurement criteria where bidimensional measurements were used to define tumor burden.²⁷ In solid cancers, RECIST is now more commonly used. RECIST uses the sum of the longest unidimensional measurement of tumor lesions as the basis of its criteria. Many have now adopted a modified RECIST-based irRC as the criteria used to measure the effect of immunotherapeutic approaches in solid cancers (see comparisons below). Nishino, *et al* prospectively examined the impact of using bidimensional vs. unidimensional measurements.³⁷ They concluded that irRC using the unidimensional measurements provided highly concordant response assessment compared with the bidimensional irRC, with less measurement variability and recommended the use of unidimensional irRC to assess response to immunotherapy in solid tumors.

Appendix Table 1 Summary of Measurement and Response Assessment Approaches for Bidimensional and Unidimensional Assessment Based on irRC

	Bidimensional assessment (the original irRC)	Unidimensional assessment
Measurable lesions	≥5 x 5 mm ² by bidimensional measurements	≥10 mm in the longest diameter
Measurement of each lesion	The longest diameter x the longest perpendicular diameter (cm ²)	The longest diameter (cm)
The sum of the measurements	The sum of the bidimensional measurements of all target lesions and new lesions if any	The sum of the longest diameters of all target lesions and new lesions if any
Response assessment	PD: ≥25% increase from the nadir PR: ≥50% decrease from baseline CR: Disappearance of all lesions	PD: ≥20% increase from the nadir PR: ≥30% decrease from baseline CR: Disappearance of all lesions
New lesions	The presence of new lesion(s) does not define progression. The measurements of the new lesion(s) are included in the sum of the measurements.	

Confirmation Confirmation by 2 consecutive observations not less than 4 weeks apart was required for CR, PR, PD

As published in Nishino et al.³⁷

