Appendix D Comparison of RECIST v1.1 vs. RECIST-based irRC

	RECIST v1.1	RECIST-based irRC
New, Measurable lesions (≥ 10 mm)	Recorded as PD	Incorporated into tumor burden (see Appendix C)
New, non-measurable lesions (< 10 mm)	Recorded as PD	Do not define progression (but preclude irCR)
Non-Target Lesions	Contributes to best overall response (CR, PR, SD, PD)	Contribute to irCR (complete disappearance required)
CR	Disappearance of all lesion in 2 consecutive observations ≥ 4 weeks apart	Disappearance of all lesions in 2 consecutive observations ≥ 4 weeks apart
PR	$\geq 30\%$ decrease in sum of the longest diameter of all index lesions compared with baseline in 2 observations ≥ 4 weeks apart, in the absence of new lesions or unequivocal progression of non-index lesions	$\geq 30\%$ decrease in tumor burden compared with baseline in 2 observations ≥ 4 weeks apart
SD	Neither sufficient shrinkage to qualify for PR or increase to qualify for PD when compared to the smallest sum of diameters while on study	30% decrease in tumor burden compared with baseline cannot be established nor 20% increase when compared with nadir
PD	$\geq 20\%$ increase in the sum of the diameters of the target lesions when compared to the smallest sum while on study. The sum must also demonstrate an absolute increase of ≥ 5 mm. The appearance of ≥ 1 new lesion is considered PD	$\geq 20\%$ increase in tumor burden compared with nadir (at any single timepoint) in 2 consecutive measurements ≥ 4 weeks apart.

CR = complete response; irRC = immune-related response criteria; irCR = immune-related complete response; PD = progressive disease; PR = partial response; RECIST = response evaluation criteria in solid tumors; SD = stable disease.

Overall Response Using the irRC

The overall response according to the irRC is derived from timepoint response assessments (based on tumor burden) as follows:

- Immune-related complete response (irCR): complete disappearance of all lesions (whether measurable or not, and no new lesions) and confirmation by a repeat, consecutive assessment no less than 4 weeks from the date first documented
- Immune-related partial response (irPR): decrease in tumor burden $\geq 30\%$ relative to baseline and confirmed by a consecutive assessment at least 4 weeks after first documentation
- Immune-related Stable Disease (irSD): not meeting criteria for irCR or irPR, in absence of irPD

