# **5 STUDY ENDPOINTS**

# 5.1 Efficacy Endpoints

# 5.1.1 Primary Efficacy Endpoint

# 5.1.1.1 **Progression free Survival (PFS)**

PFS will be based on RECIST 1.1 response guidelines modified to use irRC-specific confirmation. Progression-free survival (PFS) in months is calculated as: (date of first progression or death (any reason) – date of randomization +1)/30.4375. The irRC modification requires a confirmation of progressive disease (PD) at least 4 weeks later with imaging; once confirmed, the date of progression is defined as the first date the total tumor burden was shown to have increased by at least 20% compared with nadir. Patients without progression or death are censored at the date of the last disease assessment. If a patient begins a new anti-cancer therapy or has radiotherapy or surgery at a lesion site prior to confirmed progression (or death), the patient will be censored at the last assessment where the patient was documented as progression free prior to the intervention. Patients with two or more missing response assessments prior to a visit with progression (or death) will be censored at the last visit where the patient is documented to be progression free. Patients without disease assessment post-baseline will be censored at the randomization date. As needed, we will use Table 3 to specify how dates of progression events and dates for censoring of progression data are assigned. Table 3 represents an analysis that only includes well-documented and verifiable progression events. In Table 3, the progression dates are:

- Based only on radiological assessments verified by an IRC and symptomatic deterioration date assessed by study investigator.
- Assigned to the first time when tumor progression was noted.
- The date of death when the patient is closely followed. However, deaths occurring after two or more missed tumor assessments (> 91 days after last tumor assessment) are censored at the last visit.

Progressive disease will be assessed by the unidimensional measurements approach of the Immune-related Response Criteria.

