scheduled visits• Date of radiological assessment showing new lesion (if progression is based on new lesion); or • Date of last radiological assessment of measured lesions (if progression is based on increase in sum of measured lesions)Symptomatic deterioration before first PD assessmentDate of Symptomatic deteriorationProgressedSymptomatic deterioration between adequate assessment visitsDate of Symptomatic deteriorationProgressedSymptomatic deterioration after two or more missed visitDate of last tumor assessmentCensoredDeath before first PD assessmentDate of deathProgressedDeath between adequate assessment visitsDate of last tumor assessmentCensoredDeath or progression after two or missed visitDate of last tumor assessmentCensoredDeath or progression after two or more missed visitDate of last tumor assessmentCensoredDeath or progression after two or more missed visitDate of last tumor assessmentCensoredNew anti-cancer therapy or radiotherapy or surgery at a lesion siteDate of last tumor assessment where the patient was documented as progression free prior to the interventionCensored	Progression documented between	Earliest of:	Progressed
(if progression is based on new lesion); or • Date of last radiological assessment of measured lesions (if progression is based on increase in sum of measured lesions)Symptomatic deterioration before first PD assessmentDate of Symptomatic deteriorationProgressedSymptomatic deterioration between adequate assessment visitsDate of Symptomatic deteriorationProgressedSymptomatic deterioration after two or more missed visitDate of last tumor assessmentCensoredDeath before first PD assessmentDate of deathProgressedDeath between adequate assessment visitsDate of deathProgressedDeath or progression after two or missed visitDate of last tumor assessmentCensoredDeath or progression after two or missed visitDate of last tumor assessmentCensoredDeath or progression after two or missed visitDate of last tumor assessmentCensoredDeath or progression after two or more missed visitDate of last tumor assessmentCensoredNew anti-cancer therapy or radiotherapy or surgery at a lesion siteDate of last tumor assessment where the patient was documented as progression free prior to the intervention	scheduled visits	• Date of radiological assessment showing new lesion	

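### One row of SAP Table 3 allows progression on a new lesion alone, and dates sum-based progression at the last scan, against the SAP's own irRC rule for primary PFS

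*SAP*

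**What the plan says.** SAP 5.1.1.1 sets the criteria for the primary endpoint: "Progressive disease will be assessed by the unidimensional measurements approach of the Immune-related Response Criteria". After confirmation by imaging at least 4 weeks later, the progression date is "defined as the first date the total tumor burden was shown to have increased by at least 20% compared with nadir". The same section says that Table 3 will be used, where needed, to assign event and censoring dates.

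In Table 3, the row for progression documented between scheduled visits has the outcome of progressed and takes the earlier of two dates:

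- "Date of radiological assessment showing new lesion", on the condition that a new lesion is the basis for progression
- "Date of last radiological assessment of measured lesions (if progression is based on increase in sum of measured lesions"

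Protocol Appendix C states that only irRC determines progression and, on new lesions, "The presence of new lesion(s) does not define progression". Appendix D sets the two systems side by side. A new lesion is PD under RECIST v1.1. Under the trial's irRC a new measurable lesion is "Incorporated into tumor burden", and a new lesion under 10 mm does not count as progression.

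**The concern.** Two rules for the same primary endpoint sit in one SAP section. The text knows one route to radiographic progression, a confirmed 20% rise in total burden that already includes new measurable lesions. The Table 3 row knows two routes, one of which is a new lesion as such. The row also dates the sum-based route at the last assessment, where the text uses the first.

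The choice between them would fall to whoever programs the endpoint. It reaches primary PFS, the Kaplan-Meier 6-month PFR (SAP 5.1.2.1) and its signal rule that the lower 80% limit exceed 25% (SAP 7.6.2.1). It also reaches the progression-free counts in the two-stage futility guideline, and duration of response and of clinical benefit, which run to a PD date and borrow the PFS censoring rule.

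**Working it through.** **Step 1. The texts compared.**

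| Question | SAP 5.1.1.1 text and protocol Appendices C and D | Table 3 row |
|---|---|---|
| Can a new lesion by itself be progression? | No; it counts only through the total burden | Yes; listed apart from the sum |
| Which scan dates a rise in the sum? | First scan at least 20% above nadir, once confirmed | Last assessment of measured lesions |
| Status | Definition of the primary endpoint | Used as needed; not labelled a sensitivity analysis |

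**Step 2. When the two event rules give different answers.** Suppose one new lesion of diameter d appears and all other disease is at its nadir sum N. The burden rises by d/N. The irRC threshold is d/N ≥ 0.20, that is N ≤ 5d.

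- The smallest measurable non-nodal lesion is 10 mm (Appendix C): 5 × 10 = 50 mm. At N = 50 mm the rise is 10/50 = 20%, so both rules can call progression.
- At N = 100 mm the rise is 10/100 = 10% for a 10 mm lesion and 15/100 = 15% for a 15 mm lesion. Neither is irRC PD, yet the row supplies an event date.
- At N = 150 mm the rise is 10/150 = 6.7%.
- A non-measurable new lesion adds nothing to the sum, so the rules differ at any N.

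Sums above 50 mm are expected in this trial: eligibility allows total lesions up to 12 cm (synovial sarcoma) or 15 cm (MRCL), and SAP 7.7 has a baseline category above 50 mm.

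**Step 3. The dating limb.** If the last assessment is taken to be the confirming scan, the event moves by at least 28 days, or 28/30.4375 = 0.92 months, later than the text allows. The lead-in to Table 3 itself assigns progression to when it was first noted, so the row disagrees with its own preamble on this reading.

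**Step 4. The design figure that depends on the definition.** Inputs from protocol 10.3 and 10.3.1: PFR 25% versus 45%, at least 6 of 18 to continue, at least 14 of 40 to recommend further study.

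- Medians to PFR: 0.5^(6/3) = 25.0%; 0.5^(6/5.2) = 44.9%.
- P(success | p) = Σ from x = 6 to 18 of Bin(x; 18, p) × P(Y ≥ 14 − x), with Y ~ Bin(22, p).
- p = 0.25 gives 0.080 (stated alpha 0.10). p = 0.45 gives 0.856 (stated power 0.85). The design reproduces.

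**Step 5. Illustration only.** The documents give no rate of new-lesion-only events. Assume that a share f of all counted progressions before 6 months is new-lesion-only and not irRC PD, acting as an independent hazard. Then the PFR becomes 0.45^(1/(1 − f)).

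| Assumed f | PFR at 6 months | Two-stage probability of success |
|---|---|---|
| 0 | 45% | 0.86 |
| 10% | 0.45^(1/0.9) = 41% | 0.74 |
| 20% | 0.45^(1/0.8) = 37% | 0.56 |

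**The case against.** The strongest reply is that the row assigns dates and does not define events. It presupposes documented progression, its new-lesion line is conditional, it covers only findings between scheduled visits, and Table 3 applies only as needed. What counts as PD is fixed by the irRC sentence in the text. On that view, progression based on a new lesion simply means a new measurable lesion that carries the burden past 20%.

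The limits on reach stand. A reader might infer that Table 3 turns the whole primary PFS into a RECIST new-lesion analysis; the documents do not support that. The compatible reading is possible too, and for measurable lesions the gap closes at small nadir sums (Step 2).

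It does not remove the conflict. The row sets a rise in the sum beside the new lesion as a distinct basis, so on the compatible reading the new-lesion line would be redundant. The section never says when Table 3 applies. SAP section 8 makes the SAP prevail over the protocol, but both rules are in the SAP. The opening phrase of 5.1.1.1, RECIST 1.1 with irRC confirmation, could be taken to admit a confirmed new lesion; that adds to the ambiguity, since the dating sentence and the closing irRC sentence go by burden.

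The consequences are also bounded. Primary PFS is described arm by arm, between-arm comparisons are exploratory, the futility guideline is non-binding, and the same rule applies to both arms.

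**Conclusion.** The point holds, with limited reach. One row of Table 3 contradicts SAP 5.1.1.1 and protocol Appendices C and D, both on what can be a progression event and on which scan dates it. New-lesion events that are not irRC PD could enter primary PFS: any non-measurable new lesion, or a single new 10 mm lesion when other disease is at nadir and the nadir sum exceeds 50 mm.

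The number of patients affected is unknown and may be small. The figures in Step 5 show sensitivity and do not estimate an effect. They apply f to all early progressions, whereas the row covers only those between visits, and they assume that affected patients would not soon reach irRC PD anyway; if they would, mainly the date moves.

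Three stronger inferences should be resisted:

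- That a known amount of power is lost. No rate in the documents supports this. A single-stage calculation of at least 14 of 40 at 45% gives 0.92, but it omits the 6 of 18 first stage and is not the design's power. The 14 of 40 criterion is in the protocol and is not repeated in SAP 7.10.
- That the row defeats a stated aim of avoiding pseudo-progression. The documents do not give that as the reason for choosing irRC.
- That the SAP has deliberately replaced irRC. Its own text keeps irRC.

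**What to change.** In the Table 3 row for progression between scheduled visits:

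1. Delete the new-lesion line, or state that new lesions count only through the total burden.
2. Replace the last-assessment date with the first scan at which target plus new measurable burden is at least 20% above nadir, confirmed at least 4 weeks later. Deleting the new-lesion line alone would leave this second conflict in place.
3. State when Table 3 applies to the primary analysis. If a version counting new lesions is wanted, label it a RECIST v1.1 PFS sensitivity analysis; Appendix C says that those data are collected.

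The cost is an SAP table edit and the matching programming specification before database lock. No new data are needed, and the sample size is unchanged.

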#### Table 3 – Progression-Free Survival (Includes investigator assessment)

# 5.1.1.2 **Overall Survival (OS)**

Overall survival in months will be calculated as: (date of death (any cause) – date of randomization) +1)/30.4375. Patients who were alive at the end of study will be censored at the last date the patient is known to be alive or data analysis cutoff date, whichever is earlier.

# 5.1.2 Secondary Efficacy Endpoint

# 5.1.2.1 PFR at 6 Months

PFR at 6 months will be calculated using Kaplan-Meier method.

# 5.1.2.2 Immune response and histologic and molecular tissue changes in tumor tissue or peripheral blood

Baseline and post treatment anti-NY-ESO-1 immune response and histologic and molecular changes in peripheral blood data will be collected.

# 5.1.2.3 Time to Next Treatment (TTNT)

Time to next treatment in months will be calculated as: (start date of subsequent therapy – date of randomization) +1/30.4375. Patients who did not receive subsequent therapy will be censored at the last date the patient is known to be alive or data analysis cutoff date, whichever is earlier.

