10.2.2.4.2 Secondary Efficacy Analysis

A secondary efficacy analysis will be based on the proportion of patients that are progression-free at 6 months after start of study drug treatment (Day 0). Each treatment group will be evaluated with a Simon 2-stage design (Section 10.3.1). Time-to-next-treatment and DMFS will be compared between treatment arms based on a stratified log-rank test. The Kaplan-Meier curve will summarize TTNT graphically by treatment arm. Tabular summaries of the Kaplan-Meier curves will be provided by treatment arm.

Immune response and histologic and molecular tissue changes in tumor tissue or peripheral blood will be summarized by treatment arm.

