10.3 Interim Analysis

An exploratory analysis of the PFR at 6 months after treatment initiation will be used as a non-binding futility analysis for each treatment arm. Upon obtaining the progression status after 6 months on study from the first 36 (18 per arm) and subsequently from all enrolled patients, interim analyses will be performed and presented to the DMC, which will include estimates of PFS and assessment of PFR. Based on the assumptions in Section 10.3.1, futility guidelines at Stage 1 will be based on 18 patients and will require at least 6 patients to be progression free to

continue on to Stage 2. With an additional 22 patients at the end of Stage 2, at least 14 of the total of 40 patients should be progression free at 6 months after initial dosing to recommend further study in this setting. No formal interim analysis will be performed for efficacy. For the purposes of safety monitoring, key safety analysis will also be performed quarterly. The DMC will evaluate the available data and make necessary recommendations to the study. Details will be outlined in the DMC charter.

A final analysis will be conducted when at least 72 deaths have been observed, or sooner if the Sponsor so decides.

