10.3.1 Sample Size

The median PFS for first-line chemotherapy for patients with metastatic synovial sarcoma has been reported to be 2.5 to 8.3 months; 34 PFS with atezolizumab in the post-chemotherapy setting is unknown. Thus, no power calculations based on comparisons of PFS were made. However, based on an unacceptable and desirable median PFS of 3 months and 5.2 months, respectively, corresponding PFRs at 6 months were derived. With an unacceptable PFR of 25% and an acceptable PFR of 45% at 6 months, a Simon 2-stage design will be used to examine the PFR in 40 patients in each arm ($\alpha=0.1$, $\beta=0.15$). For this study, two groups of approximately 40 patients each (approximately 80 patients total) will be dosed with CMB305 with atezolizumab or with atezolizumab alone to assess the quartiles (25%, 50%, and 75%) of PFS with 95% confidence intervals (CIs) and the PFR at 6 months. If favorable results are observed, the study may be expanded to improve the estimates of PFS.

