# 7.6.2.3 Time to Next Treatment (TTNT)

TTNT will be analyzed using the same methods described for OS/PFS.

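### Time to next treatment (TTNT) censors patients who die untreated, with no competing-risk or composite summary beside its Kaplan-Meier curve and log-rank test

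*SAP*

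**What the plan says.** SAP 5.1.2.3 defines the endpoint: "Time to next treatment in months will be calculated as: (start date of subsequent therapy" minus the randomization date, converted to months. No other event is named. On censoring it says "Patients who did not receive subsequent therapy will be censored at the last date the patient is known to be alive", or at the data cutoff if that is earlier.

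SAP 7.6.2.3 gives the method: "TTNT will be analyzed using the same methods described for OS/PFS". In SAP 7.6.1.1 that means Kaplan-Meier medians and plots by arm, a Cox hazard ratio and a log-rank test stratified by disease type. Protocol 10.2.2.4.2 agrees: "Time-to-next-treatment and DMFS will be compared between treatment arms based on a stratified log-rank test" and "The Kaplan-Meier curve will summarize TTNT graphically by treatment arm".

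The protocol gives no event or censoring rule for TTNT, and SAP section 8 says that the SAP prevails where the two differ, so SAP 5.1.2.3 is the working definition. Neither document adds a competing-risk method, a composite or a sensitivity analysis for this endpoint.

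**The concern.** Kaplan-Meier assumes that a censored patient could still have the event later. A patient who has died cannot start another therapy. With untreated deaths censored, the curve describes neither the time patients live without a next therapy nor the share of them who receive one.

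The SAP handles death differently elsewhere. PFS (5.1.1.1) and distant metastasis-free survival (5.1.2.4) count it as an event, subject to their rules on missed assessments. Time to new lesion (5.1.3.4), which is only exploratory, is defined once without death and once with it. TTNT is a named secondary endpoint, yet it has only the version without death, and no reason is given.

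At stake is the reading of the arm comparison. Starting another therapy counts against an arm on this endpoint; dying before starting one does not.

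**Working it through.** **Inputs.** The documents state no expected TTNT, and they do not give the share of first events that are deaths without therapy. There is no plan figure to reproduce, so everything here is illustrative. Assumptions: constant cause-specific hazards; a share f of first events that are untreated deaths, varied over 10%, 20% and 30%; a reported Kaplan-Meier median of 6.0 months.

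**Formulas.** Let hN be the hazard of next therapy, hD the hazard of death without therapy, and L = hN + hD.

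- Kaplan-Meier with deaths censored: exp(-hN·t), so hN = ln 2 / 6.0 = 0.1155 per month.
- f = hD / L, so L = hN / (1 - f).
- Therapy-or-death median: ln 2 / L = 6.0 × (1 - f).
- True incidence of next therapy by time t: (1 - f) × (1 - exp(-L·t)).

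**Estimates within an arm.** At 12 months, two medians have passed, so 1 - KM = 1 - 0.25 = 75% whatever f is.

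| f | L per month | therapy-or-death median | true incidence at 12 months |
|---|---|---|---|
| 10% | 0.1284 | 5.4 months | 0.9 × (1 - 0.214) = 71% |
| 20% | 0.1444 | 4.8 months | 0.8 × (1 - 0.177) = 66% |
| 30% | 0.1650 | 4.2 months | 0.7 × (1 - 0.138) = 60% |

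**Direction depends on the target.** At f = 20%, the true incidence reaches 50% when exp(-L·t) = 1 - 0.5/0.8 = 0.375, so t = 0.981 / 0.1444 = 6.8 months. The Kaplan-Meier median of 6.0 months is later than the therapy-or-death median (4.8) and earlier than the cumulative-incidence median (6.8).

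**Comparison between arms.** Take untreated-death shares of 30% in arm A and 10% in arm B.

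- Equal therapy-or-death hazards: the TTNT hazard ratio, A to B, is (1 - 0.30)/(1 - 0.10) = 0.78, in favour of the arm with more untreated deaths.
- Equal next-therapy hazards: the TTNT hazard ratio is 1.00, while the therapy-or-death hazard ratio is 0.90/0.70 = 1.29 against arm A.

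**Simulation check.** Trials of 80 patients, cut at the 72nd death, were simulated 1,000 times per setting. The true therapy-or-death median was set at 5.2 months (borrowed from the PFS assumption purely as a scale), and survival after next therapy was assumed to have a 12-month median. At f = 10/20/30%, the mean Kaplan-Meier median with deaths censored was 5.79/6.61/7.55 months, against 5.78/6.50/7.43 from 5.2/(1 - f). Untreated deaths averaged about 8, 16 and 24.

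**The printed formula.** "start date of subsequent therapy – date of randomization) +1/30.4375" divides only the 1. For a difference of 160 days it gives 160 + 1/30.4375 = 160.03; the intended value is (160 + 1)/30.4375 = 5.29 months.

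**The case against.** The case for leaving the plan alone has real content.

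- **The log-rank test is legitimate.** With deaths censored it tests the cause-specific hazard of starting next therapy, which is an interpretable quantity. A reader might infer that the test is invalid or that it overstates TTNT. It estimates no time, so it cannot. This stands; what is missing is a label and a companion summary.
- **The direction is not one-sided.** A reader might say flatly that TTNT is overstated. That is true against time to therapy or death and reverses against cumulative incidence. This stands, so any statement of direction must name its target.
- **Mortality.** Protocol 10.3 says "A final analysis will be conducted when at least 72 deaths have been observed, or sooner if the Sponsor so decides", and Protocol 10.3.1 plans "two groups of approximately 40 patients each (approximately 80 patients total"). A reader might take 72/80 = 90% as the expected mortality and as the size of the problem. The documents do not support that: 72 is an analysis trigger that the sponsor may cut short, and deaths after next therapy do not affect TTNT at all.
- **Deaths are not hidden from the trial.** OS is a primary endpoint and counts them all, PFS counts death subject to its censoring rules, and SAP 7.8.2 tabulates deaths. This stands; the omission lies within TTNT only.
- **Stakes.** Protocol 10.4 treats all p-values as nominal, SAP 7.9 calls between-arm comparisons exploratory, and no decision rule hangs on TTNT. This limits the importance.
- **Size.** The share of untreated deaths is assumed, and the between-arm distortion arises only if deaths without therapy differ between arms. Both points stand.

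None of this makes the TTNT curve readable as printed. Neither quantity a reader would take from it is what it estimates.

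**Conclusion.** The point holds in a limited form. As written, TTNT censors untreated deaths, and nothing elsewhere in the plan supplies the missing summary. Under constant hazards, with untreated deaths at 10 to 30% of first events, the Kaplan-Meier median exceeds the therapy-or-death median by a factor of 1/(1 - f), that is by 11 to 43%. The 12-month complement of the curve is 4 to 15 percentage points above the true incidence when it reads 75%. With shares of 30% and 10% in the two arms, the TTNT hazard ratio can be 0.78 in favour of the arm with more untreated deaths although the therapy-or-death hazards are equal. The true shares are unknown, so these figures show how the distortion scales and do not forecast it. The consequence is a misleading secondary summary; the primary endpoints are untouched. The bracket error is clerical: the text says months, and the PFS and DMFS formulas are bracketed correctly.

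**What to change.** Amend SAP 5.1.2.3 and 7.6.2.3 as follows:

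1. Report TTNT as the cumulative incidence of next therapy by arm, with death without therapy as a competing event.
2. Add time to next anti-cancer therapy or death from any cause, censoring only patients alive without therapy, and show its two components.
3. Tabulate by arm the number of patients who died without subsequent therapy.
4. Keep the stratified log-rank test if wished, labelled as a comparison of the cause-specific hazard of next therapy.

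Separately, as an editorial correction, write the formula as (date – randomization date + 1)/30.4375, and repair the similar unbalanced bracket in the OS formula (SAP 5.1.1.2).

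The cost is SAP wording and a little extra programming. Survival status, death dates and subsequent treatments are already collected (Protocol 8.2.4 and 9.4.7; SAP 7.8.11). The one downside is that the composite mixes two different events, which is why its components should be shown.
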